APPENDIX C. ASTHMA CONTROL QUESTIONNAIRE (ACQ)

38

GLOSSARY OF ABBREVIATIONS

ACQ	Asthma Control Questionnaire
AE	Adverse Event
API	Active Pharmaceutical Ingredient
AQLQ	Asthma Quality of Life Questionnaire
AR	Adverse Reaction
ATS	American Thoracic Society
BAL	Bronchoalveolar Lavage
BEC	Bronchial Epithelial Cell
BTS	British Thoracic Society
CRF	Case Report Form
CRP	C-Reactive Protein
CRTH2	Chemoattractant Receptor-Homologous molecule expressed on Th2 cells
DMP	Data Management Plan
ECG	Electrocardiogram
EDTA	EthyleneDiamine Tetraacetic Acid
ELF	Epithelial Lining Fluid
ELISA	Enzyme-Linked ImmunoSorbent Assay
FACS	Fluorescence-Activated Cell Sorting
FeNO	Fraction of exhaled Nitric Oxide (NO)
FEV ₁	Forced Expiratory Volume in One Second
FVC	Forced Vital Capacity
GCP	Good Clinical Practice
ICS	Inhaled Corticosteroid
IgE	Immunoglobulin E
IL	Interleukin
IMP	Investigational Medicinal Product
IUD	Intrauterine device
IUS	Intrauterine system
JRCO	Joint Research Compliance Office
LABA	Long Acting Beta Agonist
LRT	Lower Respiratory Tract
MDI	Metered Dose Inhaler
MHRA	Medicines and Healthcare Products Regulatory Agency
mRNA	Messenger Ribonucleic Acid (RNA)
MSD	Meso Scale Discovery [a multiplex immunoassay]
PC ₂₀	Provocation concentration [of histamine] producing a 20% fall in FEV ₁
PEF	Peak Expiratory Flow
PGD ₂	Prostaglandin D ₂
PHA	Phytohemagglutinin
PPB	Parts Per Billion
qPCR	Quantitative Polymerase Chain Reaction (PCR)
REC	Research Ethics Committee
RV	Rhinovirus
RV-16	Rhinovirus serotype 16
SABA	Short Acting Beta Agonist
SAE	Serious Adverse Event
SAM	Synthetic Absorptive Matrix
SAP	Statistical Analysis Plan
SAR	Serious Adverse Reaction

SOB	Shortness Of Breath
SUSAR	Suspected Unexpected Serious Adverse Reaction
TCID ₅₀	Tissue culture infective dose = the amount of pathogenic agent to produce a pathological change in 50% of cell cultures inoculated
TLC	Total Lung Volume

KEYWORDS

Rhinovirus, Asthma, Exacerbation, PGD2, CRTH2

STUDY SUMMARY

TITLE Effect of OC459 on the Response to Rhinovirus Challenge in Asthma.

DESIGN Randomised, double-blind, placebo-controlled, parallel group study.

AIMS To evaluate if the oral CRTH2 antagonist OC459 is effective in preventing and/or treating rhinovirus-induced asthma exacerbations.

OUTCOME MEASURES Primary outcome: difference in symptom scores after rhinovirus infection.

Secondary outcomes: measures of health status, lung function, airway hyper-responsiveness, exhaled nitric oxide (FeNO) levels, virus load, and other laboratory parameters (e.g. differential cell counts, levels of cytokine/biomarker proteins and mRNA in respiratory samples).

[figure not shown]
POPULATION 44 adults with asthma (of which 30 will be evaluable).

ELIGIBILITY Adult subjects with moderate persistent asthma who meet the inclusion/exclusion criteria described.

TREATMENT OC459 or placebo, for a total of 5 weeks per subject.

DURATION 27 months

FIGURE: STUDY OVERVIEW

1 INTRODUCTION

1.1 BACKGROUND

Importance of asthma and asthma exacerbations

Asthma is a long-term condition affecting the airways in the lungs, causing symptoms in patients such as breathlessness, wheeze, tightness in the chest and cough. Asthma is the most prevalent chronic respiratory disease, affecting 5-10% of adults with a further 30% of school age children reporting wheeze [1]. Although some children will outgrow their asthma, future prevalence is predicted to rise: the WHO estimate 300 million people worldwide are affected by asthma and that this is likely to increase to 400 million cases over the next 15-20 years [2].

The major morbidity, mortality and health care costs related to asthma are a result of periods of acutely increased symptomatology, called 'exacerbations' [3]. Acute exacerbations of asthma are an enormous problem to adults and children: ~5-10% of asthmatics have been hospitalised with an exacerbation and 60% have had an exacerbation in the previous year [4]. Asthma mortality in the UK is ~2,000 per annum – extrapolated to Europe, this means approximately ~25,000 people die unnecessarily of asthma each year. The financial cost of exacerbations is estimated to be ~50% of total expenditure on asthma care [5].

Lack of effective treatments for asthma exacerbations

Currently available therapies, predominantly inhaled corticosteroids and bronchodilators, prevent only ~40% of asthma exacerbations [6]. These figures are in the context of clinical trials – in real life asthma exacerbations are even less likely to be prevented: >50% of European asthma patients reported having an exacerbation in the last year with >1/3 children and >1/4 adults requiring urgent medical care visits as a result [7]. The vast majority of asthma exacerbations therefore continue to occur despite use of the best available current therapies.

When exacerbations do occur, treatment options are limited and have developed little in recent years. Treatment involves increasing doses of inhaled bronchodilators and systemic/oral steroids – more of the same drugs that failed to prevent the exacerbations occurring. Furthermore these treatments do not address the causes or mechanisms driving the exacerbations. Current preventive and therapeutic strategies are thus of limited efficacy and development of new approaches is urgently needed.

Causes and mechanisms of asthma exacerbations

The causes of asthma exacerbations are complex and likely to involve one or more of a number of factors including poor control of underlying disease, allergen exposure and viral infection. Respiratory viral infections appear the dominant individual precipitant as they are detected in the great majority of asthma exacerbations in both children (80-85%) and adults (60-80%) [8]. The most commonly detected viruses are human rhinoviruses (~60-80%), and it has been shown that experimentally infected asthmatics with rhinovirus (RV) precipitates an acute exacerbation [9].

The use of experimental RV infection has enabled the study of the mechanisms of asthma exacerbations. These have shown that RV infection leads to increased levels of inflammatory mediators in asthmatic subjects relative to healthy controls (specifically 'type 2 cytokines' e.g. IL-4, IL-5 and IL-13, as well as IL-33 and Prostaglandin D₂), and that these increases correlate with the severity of respiratory symptoms [10]. New treatments have subsequently been developed to targeting those mediators, e.g. an antibody against IL-5 [11].

Studies *in vitro* have found that the binding of Prostaglandin D₂ (PGD₂) to the CRTH2 receptor on inflammatory cells (e.g. Th2 lymphocytes, type 2 innate lymphoid cells) stimulates them to produce the type 2 cytokines implicated in asthma exacerbations [12, 13]. Thus treatment with a CRTH2 antagonist represents an attractive approach to prevent RV-mediated exacerbations in asthmatic patients.

1.2 RATIONALE FOR CURRENT STUDY

Hypothesis: This trial is designed to investigate the hypothesis that CRTH2 antagonism can prevent or attenuate the deterioration in symptoms in patients with asthma (i.e. asthma exacerbations) following rhinovirus infection.

Rationale for using the RV-induced asthma exacerbation model

The RV-induced asthma exacerbation model offers the ability to investigate treatment effects on exacerbations with a small number of volunteers, minimising the numbers exposed to a novel agent with limited safety data. In contrast, trials of therapies powered to evaluate an effect on naturally occurring exacerbations require several hundred volunteers, a long study period to capture enough events and are significantly more expensive to carry out.

The RV-induced exacerbation model has been used extensively around the world over >15 years, including four studies by [name] group [9, 10, 14, 15], and is well-established with an excellent safety profile (reviewed in [16]); across the studies at Imperial there have been no adverse events, and no need for hospitalisation or systemic corticosteroids during the infection. Moreover, the RV-induced exacerbation model uniquely provides the opportunity to select a well-defined sample population, use a uniform viral challenge, and sample repeatedly as the exacerbation evolves, allowing accurate dissection of the timings of responses and their relationship to viral load.

Rationale for using the CRTH2 antagonist OC459

As of August 2013, at least 12 CRTH2 antagonists were in active clinical development [17]. Of these, OC459 (Atopix Therapeutics Ltd) had been trialled for the longest duration in a phase 2 study (17 weeks). In total, 637 patients across five published studies have been exposed to OC459 [18-22], including 482 patients with asthma, with an excellent safety record. OC459 has therefore been chosen for further study from the available CRTH2 antagonists due to its safety profile; there is no reason to think that is more or less effective than any other CRTH2 antagonist.

In addition, the largest study of OC459 to date suggested that it may be effective in reducing exacerbations: a trend towards reduction in asthma exacerbations was noted, with a 3.8% incidence in the pooled dose groups compared to 7.7% on placebo ($p=0.107$) [22]. A dose of 25 mg once daily was as effective as the other doses (100mg twice daily and 200mg once daily) in this study.

2 STUDY OBJECTIVES

Primary objective:

- To assess the impact of OC459 on Total Lower Respiratory Tract Symptoms Score after rhinovirus infection (sum of daily scores day 0 to day 14)

Secondary objectives:

- To assess the impact of OC459 on other clinical and laboratory parameters during rhinovirus infection:
 - Health status (assessed by Asthma Control Questionnaire (ACQ) scores)
 - Lung function (assessed by spirometry)
 - Airway inflammation (assessed by exhaled nitric oxide (FeNO) levels)
 - Airway hyperresponsiveness (assessed as the provocation concentration of histamine producing a 20% fall in FEV₁, or PC₂₀)
 - Viral load (measured by quantitative Polymerase Chain Reaction (qPCR) on nasal lavage samples)
- To determine the mechanism of action of OC459, by assessing the impact of OC459 on the following during rhinovirus infection:
 - Eosinophil recruitment (measured by cell counts in sputum and bronchoalveolar lavage (BAL); eosinophil products, e.g. Eosinophil Cationic Protein (ECP), in BAL)
 - Recruitment of other immune cells (e.g. ILC2, Th2) implicated in the prostaglandin D₂ / type 2 inflammatory pathway to the airways and/or airway mucosa (measured by flow cytometry to sort and count cells in BAL, serum and nasal scrapes; and immunohistochemistry staining of bronchial biopsies)
 - Release of inflammatory mediators implicated in the prostaglandin D₂ / type 2 inflammatory pathway (e.g. the type 2 cytokines IL-4, IL-5, IL-13; measured by multiplex immunoassay on nasosorption, nasal lavage, bronchosorption and BAL, and mRNA analysis of cells in BAL and biopsies)
- To assess whether OC459 is able to restore deficient innate antiviral responses
 - Production of cytokines (e.g. interferon (IFN) α and λ) and expression of cytokine mRNA in cells from samples (blood, BAL) and infected with rhinovirus *ex vivo*
- To assess the safety of OC459
 - Adverse event reporting, physical examinations, vital signs, and clinical laboratory parameters

3 STUDY DESIGN

Type of study: This is a phase 2a, randomised, double-blind, placebo-controlled, parallel group study.

Study duration: The trial will take place over a 33 month period. On an individual basis, the trial will last for 9 weeks from randomisation. The trial will be considered complete when the last patient recruited completes the final visit.

Population size: 44 asthmatic subjects.

3.1 STUDY OUTCOME MEASURES

Primary outcome:

- Difference in Total Lower Respiratory Tract Symptoms Score after RV infection (sum of daily scores day 0 to day 14) between OC459 and placebo groups.

Secondary outcomes:

- Difference between OC459 and placebo groups in the following (all measured as peak and change from baseline):
 - Increase in ACQ score (health status)
 - Reduction in Forced Expiratory Volume in 1 second (FEV₁) or Peak Expiratory Flow (PEF) on spirometry
 - Increase in FeNO
 - Decrease in PC₂₀
 - Virus load in nasal lavage – total (area under the curve) for days 2-5+7+10, as well as peak and difference from baseline
 - Increase in sputum eosinophilia
 - Leukocyte numbers (e.g. ILC2, Th2) in FACS-sorted BAL, serum and nasal scrapes, and in immunohistochemistry-stained biopsies
 - Cytokine levels (e.g. IL-4, IL-5, IL-13) in nasosorption, nasal lavage, bronchosorption, BAL
 - mRNA expression of same cytokines in cells in BAL and bronchial biopsies
 - In *ex vivo* studies, protein and mRNA levels of antiviral cytokines (e.g. IFN- α , IFN- λ) produced by cells from blood, BAL, and bronchial brushings in response to rhinovirus infection
- Difference in number of adverse events in OC459 and placebo groups

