7 INVESTIGATIONAL MEDICINAL PRODUCT (IMP)

7.1 IMP DESCRIPTION

OC459 is a once-daily oral, highly potent and selective CRTH2 antagonist which is active on both the recombinant and native human receptor.

The integrated safety database for OC459 includes data for a total of 754 subjects who received OC459 for up to 3 months with more than 500 subjects receiving doses ≥ 100 mg daily. The overall incidence of adverse events was similar for those treated with OC459 (28.2%) compared to placebo (26.7%) and few subjects in either group had serious adverse events (0.1% and 0.5% for OC459 and placebo respectively). The adverse event profile after OC459 administration was generally comparable to that after placebo; the most common adverse event reported was headache (6.6% vs 5.1% for OC459 and placebo, respectively).

OC459 repeat doses of up to 400mg have been studied in patients and no clear dose ordered effects on safety have been observed. Furthermore, no end organ toxicology or significant changes in clinical chemistry (including liver enzymes) have been observed in non-clinical toxicology studies including long term studies conducted at very high doses in the mouse (3 month dosing), rat (six months dosing) and the dog (12 month dosing). The known metabolites of OC459 have been detected in at least one species including the acylglucuronide of OC459 which is the major metabolite in humans.

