8 PHARMACOVIGILANCE

8.1 DEFINITIONS

Adverse Event (AE): any untoward medical occurrence in a patient or clinical trial subject administered a medicinal product and which does not necessarily have a causal relationship with this treatment. *An AE can therefore be any unfavourable and unintended sign (including an abnormal laboratory finding), symptom, or disease temporally associated with the use of an investigational medicinal product (IMP), whether or not considered related to the IMP.*

Adverse Reaction (AR): all untoward and unintended responses to an IMP related to any dose administered. *All AEs judged by either the reporting investigator or the sponsor as having reasonable causal relationship to a medicinal product qualify as adverse reactions. The expression reasonable causal relationship means to convey in general that there is evidence or argument to suggest a causal relationship.*

Unexpected Adverse Reaction: an AR, the nature or severity of which is not consistent with the applicable product information (eg investigator's brochure for an unapproved investigational product or summary of product characteristics (SmPC) for an authorised product). *When the outcome of the adverse reaction is not consistent with the applicable product information this adverse reaction should be considered as unexpected. Side effects documented in the SmPC which occur in a more severe form than anticipated are also considered to be unexpected.*

Serious Adverse Event (SAE) or Serious Adverse Reaction: any untoward medical occurrence or effect that at any dose:

- **Results in death.**
- **Is life-threatening** – *refers to an event in which the subject was at risk of death at the time of the event; it does not refer to an event which hypothetically might have caused death if it were more severe.*
- **Requires hospitalisation, or prolongation of existing inpatients' hospitalisation.**
- **Results in persistent or significant disability or incapacity.**
- **Is a congenital anomaly or birth defect.**

Medical judgement should be exercised in deciding whether an AE/AR is serious in other situations. Important AE/ARs that are not immediately life-threatening or do not result in death or hospitalisation but may jeopardise the subject or may require intervention to prevent one of the other outcomes listed in the definition above, should also be considered serious.

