8.3 REPORTING PROCEDURES

All adverse events should be reported. Depending on the nature of the event the reporting procedures below should be followed. Any questions concerning adverse event reporting should be directed to the study coordination centre in the first instance. A flowchart is given below to aid in the reporting procedures.

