9.4 CLINICAL SYMPTOM SCORES (INCLUDING ACQ)

Patients will be required to keep a diary card of both upper and lower respiratory tract symptoms during the study period (see Appendices). The diary cards will be commenced 21 days prior to inoculation (on day -21) to derive a baseline symptom score. Symptom scores will be kept daily for 6 weeks post-inoculation until the convalescent visit. Spirometry measurements and drug compliance will be recorded on the same diary cards.

Upper Respiratory Tract Symptoms

The diary card of upper respiratory tract symptoms will be started 21 days prior to inoculation. A total upper respiratory clinical symptom score will be derived using a scale of 0 to 3 (absent, mild, moderate and severe) for each of the following eight respiratory symptoms: sneezing, headache, malaise, fever/chills, nasal discharge, nasal obstruction, sore throat and cough, according to previously established criteria [23]. Symptoms will be recorded at the same time of day and before any procedures such as bronchoscopy are performed. An example is shown below:

Symptom	Day 1	Day 2	Day 3	Day 4	Day 5	Day 6	Day 7
Sneezing							
Headache							
Malaise							

Fever/chills							
Nasal discharge							
Nasal obstruction							
Sore throat							
Cough							
Total score							

0 = absent, 1 = mild, 2 = moderate, 3 = severe

The maximum clinical severity score on any one day would be 24. Individual symptom scores will be accumulated over the six-day period from the onset of the cold and the recording on the day prior to inoculation subtracted. Thus, for a patient who has a score of zero on day -1 prior to inoculation, the maximum cumulative score for the six days is 144.

Lower Respiratory Tract Symptoms

A diary card of lower respiratory tract symptoms will be completed with a scoring system as outlined below:

Symptom	Day 1	Day 2	Day 3	Day 4	Day 5	Day 6	Day 7
Cough on waking							
Wheeze on waking							
Daytime cough							
Daytime wheeze							
Daytime breathlessness							
Nocturnal cough, wheeze, breathlessness							
Total score							

0 = absent, 1 = mild, 2 = moderate, 3 = severe

An exacerbation of asthma is defined as an increase in the total respiratory score of at least 2 points over baseline on 2 consecutive days.

Asthma Control Questionnaire (ACQ)

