9.14 BRONCHOSCOPY

Bronchoscopies will be performed on study visits as per Table 1 in the endoscopy suite at St Mary's Hospital, in accordance with British Thoracic Society (BTS) guidelines [26]:

- Subjects will sign a consent form on entering the study and will sign a separate consent form for each bronchoscopy. The procedure will be explained during the assessment stage and subjects will be given written information specifically regarding bronchoscopies in addition to the Participant Information Sheet.
- Subjects will fast for six hours prior to the procedure.
- Resuscitation equipment (for intubation, ECG monitoring and defibrillation) and necessary drugs (salbutamol, theophylline, adrenaline, hydrocortisone) will be available in the bronchoscopy room.
- Premedication will be given including:
 - Nebulised salbutamol 2.5mg prior to bronchoscopy
 - Sedation with midazolam (2-10mg) and/or fentanyl (25-200mcg) as necessary
 - Lignocaine spray (10%) and solutions (1%) for topical anaesthesia. The total dose will not exceed 7mg/kg or 400mg in total.
- Supplemental oxygen at a rate of 2Lmin⁻¹ is given via a nasal cannula and oxygen saturations and heart rate are monitored with a pulse oximeter continuously. Intravenous access will be mandatory in all cases.
- The subject will be monitored during the bronchoscopy by a separate nurse and a second suitably qualified physician will be present to act as an advocate.
- The following samples will be collected in this order:
 1. Bronchosorption using Synthetic Absorptive Matrix (SAM)
 2. Bronchial brushings
 3. Bronchoalveolar lavage (BAL)
 4. Bronchial biopsy

At the second bronchoscopy, sampling should be performed on the contralateral side to the analogous procedures done at the first bronchoscopy.

- All adverse events (pain, bleeding, hypoxia etc) will be recorded.
- Subjects will be observed for 1-2 hours, nil by mouth, after the procedure.
- Transportation will be arranged as subjects should not drive on the day of the procedure.
- All subjects will have a contact telephone number on discharge.

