7.3.4. Safety Analysis

Adverse events will be summarised by treatment and severity. Separate tables summarising adverse events and their relationship to study treatment as well as summarising adverse events by treatment and timepoint will also be produced.

Serious adverse events will be listed and summarised by site, category and treatment. Separate tables will also be produced summarising serious adverse events and their relationship to study treatment as well as summarising serious adverse events by treatment and timepoint.

Vital Signs and Laboratory blood tests will be summarized by treatment per visit and will be presented as means and standard deviations if data is consistent with that from a normal population distribution, and as medians and inter-quartile ranges for data that is inconsistent. Categorical variables will be presented as frequencies and percentages.

If it is deemed appropriate, treatment effect will be assessed via t-test for continuous variables and Chi-square test or Fisher exact test for categorical variables (with the appropriate generalized linear model being used).

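### The planned adverse-event comparison has no rule or table that separates bronchoscopy and virus-challenge events from other adverse events, so a drug-related difference can be diluted and, under conditions the documents leave open, masked

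*Protocol*

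**What the plan says.** Protocol 3.1 lists as a secondary outcome the "Difference in number of adverse events in OC459 and placebo groups". Protocol 8.1 defines an AE to include "any unfavourable and unintended sign (including an abnormal laboratory finding), symptom, or disease temporally associated with the use of an investigational medicinal product", related to the drug or not. Protocol 8.3 says "All adverse events should be reported", and 8.3.1 makes recording of non-serious events independent of whether they were expected. For bronchoscopy, Protocol 9.14 is explicit: "All adverse events (pain, bleeding, hypoxia etc) will be recorded".

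Under Protocol 9.1, drug or placebo runs daily from day -21 to day 14. Within that window come a bronchoscopy on day -8, RV-16 inoculation on day 0 and a second bronchoscopy on day 5. Protocol 9.4 scores "sneezing, headache, malaise, fever/chills, nasal discharge, nasal obstruction, sore throat and cough" in the cold diary, alongside chest symptoms. Protocol 7.1 reports that in the OC459 safety database "the most common adverse event reported was headache".

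SAP 7.3.4 plans that "Adverse events will be summarised by treatment and severity", with further tables by relationship and by timepoint. A test of treatment effect is optional. SAP 6.3.3 records AEs as uncoded free text. The Table 3.23 shell has four rows: Pre-Treatment (Wk1), Pre-Inoculation (Wk2), Assessment Phase (Wk3-4) and Follow-Up (Wk5-9).

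**The concern.** Every subject who follows the schedule is deliberately given a cold and has two bronchoscopies while on study drug. If the resulting events enter the AE count, that count has three sources: drug, virus and procedure. Procedure events should be about equal in both arms, so they add noise. Virus events are the ones the drug is meant to reduce, so they could pull the count in the opposite direction to a harm. Headache shows the overlap: it is a scored cold symptom and also the most common AE in the OC459 database.

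The plan already recognises the problem on the efficacy side. SAP 7.3.1 corrects the chest score on days 5 and 6 for symptoms attributed to bronchoscopy. The safety analysis has no counterpart. At stake is whether the named AE outcome can be read as evidence about the drug.

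**Working it through.** **1. Is there a planned figure to reproduce?** None is given for the AE comparison. The only design figure that matters here is the arm size. With SD 21.15, a difference of 22.21, two-sided 5% and 80% power: n = 2 × (1.960 + 0.842)² × (21.15/22.21)² = 14.24, so 15 evaluable per arm, as stated. At 80% infection, 15/0.8 = 18.75; the stated 22 then implies about 14-15% drop-out. I use 22 per arm below.

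**2. Which challenge events are AEs?**
- Bronchoscopy events: yes, by Protocol 9.14.
- Virus symptoms: unsettled. Protocol 8.1 covers any "symptom, or disease temporally associated with the use of an investigational medicinal product (IMP), whether or not considered related to the IMP", and 8.3 and 8.3.1 exempt nothing. Against that, the definition requires the event to be unintended, and Protocol 1.2 says the site's earlier challenge studies had no adverse events although they induced colds. No section resolves this.

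**3. Do the planned tables separate the sources?**
- *Severity (Table 3.24):* no; it ignores cause.
- *Relationship (Table 3.25):* only in part. The Protocol 8.2 scale grades relationship to trial medication. Another explanation may lower the grade, but there is no category for virus or procedure.
- *Timepoint (Table 3.23):* no. The SAP does not define week 1. Assuming weeks run from randomisation, week = floor((day + 21)/7) + 1:

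| Row | Days covered | Problem |
|---|---|---|
| Pre-Treatment (Wk1) | -21 to -15 | Already on treatment |
| Pre-Inoculation (Wk2) | -14 to -8 | Contains the first bronchoscopy |
| Assessment Phase (Wk3-4) | -7 to 6 | Mixes 7 days before inoculation with days 0 to 6 |
| Follow-Up (Wk5-9) | 7 to 41 | Includes days 7 to 14 on treatment |

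Shifting the origin does not help: the rows allow two weeks before the assessment phase, while the on-treatment run-in is three.

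**4. Illustration on counts (assumed rates).** Background AEs per subject: -ln(1 - 0.267) = 0.31, from the 26.7% placebo incidence in Protocol 7.1. Assume the drug adds 0.5 AEs per subject, and that each infected placebo subject (80%) has m challenge AEs, reduced on OC459 by a fraction r. Then

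- placebo mean = 0.31 + 0.8m
- OC459 mean = 0.31 + 0.5 + 0.8m(1 - r)
- z = difference / √((sum of the two means)/22), treating counts as Poisson
- power to show an excess = Φ(z - 1.96)

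| m | r | Placebo | OC459 | Difference | Power |
|---|---|---|---|---|---|
| 0 | – | 0.31 | 0.81 | +0.50 | 60% |
| 1 | 0 | 1.11 | 1.61 | +0.50 | 30% |
| 2 | 0 | 1.91 | 2.41 | +0.50 | 20% |
| 4 | 0 | 3.51 | 4.01 | +0.50 | 14% |
| 2 | 0.25 | 1.91 | 2.01 | +0.10 | 4% |
| 2 | 0.5 | 1.91 | 1.61 | -0.30 | 0.3% |

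Rows with r = 0 show pure dilution: the difference stands but the noise grows. Bronchoscopy events equal in both arms act in the same way. Rows with r > 0 show masking. The offset is 0.8 × m × r per subject: from 0.08 (m = 1, r = 0.1) to 1.6 (m = 4, r = 0.5), or about 2 to 35 events in an arm of 22.

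**5. Illustration on subjects with any AE.** Let c be the share of infected placebo subjects with a challenge AE, and let the drug add an independent AE risk of 0.20. Placebo risk = 1 - 0.733(1 - 0.8c); OC459 risk = 1 - 0.733 × 0.80 × (1 - 0.8c(1 - r)).

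| c | r | Placebo | OC459 | Difference (points) |
|---|---|---|---|---|
| 0 | – | 26.7% | 41.4% | +14.7 |
| 0.8 | 0 | 73.6% | 78.9% | +5.3 |
| 0.4 | 0.5 | 50.2% | 50.7% | +0.6 |
| 0.8 | 0.5 | 73.6% | 60.1% | -13.5 |

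Even the uncontaminated +14.7 points has only about 17% power at 22 per arm.

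**The case against.** The best reply is that the documents never say cold symptoms are entered as AEs. An induced cold is arguably intended, which takes it outside the definition, and the statement in Protocol 1.2 fits a practice of not counting it. The planned separation is the relationship grade, assigned by blinded investigators who may cite other explanations. Safety also rests on serious events, vital signs and laboratory tests, and the AE test is optional. Bronchoscopy affects both arms alike.

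Most of this stands as a limit on the claim. A reader might infer that challenge symptoms *are* counted and that a real harm *will* be cancelled. The documents do not support that: counting is explicit only for bronchoscopy, and cancellation also needs an effective drug. A reader might also take a dramatic loss of power as established, for example detection of an excess falling from about 68% to 2%. That result follows from an assumed tripling of other AEs (0.3 to 0.9 per subject), with 2 challenge AEs per placebo subject and a 30% reduction chosen so that totals are equal (2 + 0.3 = 2.3; 1.4 + 0.9 = 2.3). Protocol 7.1 reports 28.2% v 26.7%, a ratio of about 1.06, and gives no basis for tripling.

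What does not stand is that the existing tables suffice. Bronchoscopy events are mixed in by rule, the recording of virus symptoms is left to individual judgement, the relationship scale has no place for virus or procedure, and the week rows do not fit the schedule.

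**Conclusion.** The point holds as a gap in specification. The AE outcome is unrestricted, it includes bronchoscopy events, and it may include virus symptoms. No planned table separates these from other AEs. Dilution follows to the extent that such events are recorded. Masking is possible only if cold symptoms are entered as AEs and OC459 reduces them. The size cannot be determined from the documents; the figures above show direction and range under assumed rates and independent sources of AEs.

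The repair makes the comparison easier to interpret. It will not make 22 per arm adequate to detect a modest harm. It is a worthwhile, low-cost improvement, and the gap does not invalidate the wider safety assessment.

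**What to change.** 1. State in Protocol section 8 and SAP 7.3.4 whether diary-scored cold and chest symptoms are entered as AEs.
2. At blinded review, flag each AE as a bronchoscopy event, a diary-scored symptom after inoculation, or other. With uncoded free text, this must be done before unblinding.
3. Redefine the Table 3.23 periods by study day: day -21 to before inoculation; day 0 to 14 on treatment; after day 14. Use the same periods in Table 3.27, which has the same rows.
4. Present Tables 3.23-3.25 and the between-arm comparison twice: for all AEs, and without the flagged events.

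Do not drop the flagged events from the safety comparison. A drug-caused headache or wheeze after inoculation would then be filed as challenge response. Under the assumed tripling described above, misfiling a quarter to a half of other AEs lowers the roughly 68% power of the separated comparison to about 53% to 36%. Showing both versions avoids relying on the classification.

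The cost is one flag per AE in a trial of 44 subjects, some SAP wording and extra table strata. The downside is that some events need judgement to classify. Listings and expedited reporting stay unchanged.
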